Study objectives	
Primary Objective
 
Absolute pain score 24h after surgery, assessed by 100mm visual analogue score (VAS).
 
Secondary Objectives
 
Minimal Clinically Important Difference [MCID] in visual analogue score; VAS adjusted for pain severity; postoperative morbidity; opioid use; heart rate variability [explanatory variable].

Study design	Phase II, single-centre, two-arm, parallel group randomised controlled trial
Setting	Surgical services of hospitals undertaking major trauma orthopaedic surgery.
Participants	
Inclusion criteria
 
 • Scheduled to undergo major elective or urgent (not requiring intervention in <24h) noncardiac (orthopaedic) surgery under general and/or spinal anaesthesia, expected to take >120 minutes from the induction of anaesthesia. • American society of Anaesthesiologists (ASA) grade I–III. • Aged 18 years and over. 
Exclusion criteria
 
 • Requiring invasive mechanical ventilation and/or new renal replacement therapy during hospitalization. • Cardiac arrhythmia requiring therapy prior to/during hospitalization. • Dementia. • Cancer requiring active/ongoing therapy. • Postural orthostatic tachycardia syndrome. • Lower limb neuromuscular disorders. • Auricular dermatitis. • Day-case surgery, not requiring overnight hospital admission.
Interventions	
Sham Group: Patients randomised to receive sham treatment will receive no current via the bilateral auricular leads for 50 minutes.
 
Stimulation Group: Patients randomised to receive stimulation will receive a sub-threshold current via the bilateral auricular leads for 50 minutes.

Primary outcome measure	The primary outcome is absolute pain score 24h after surgery, assessed using the 100mm visual analogue score.

Outcome measures

Primary outcome measure

The primary outcome will be the absolute VAS pain score 24h after surgery.

Secondary outcome measures

Minimally Clinical Important Difference: The proportion of participants who achieve a minimally clinical relevant reduction >10mm using the 100 mm pain Visual Analogue Score will be compared before and after the period of stimulation in each group, before and after surgery.[1]

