VAS stratified by pain intensity: Absolute changes in pain score before and after sham/stimulation will be compared before and after the period of stimulation in each group before and after surgery, stratifying for mild, moderate, and severe pain intensity before the intervention. A pain VAS score of 30, 70, and 100 indicates the upper boundaries of mild, moderate, and severe pain intensity.[1]

Postoperative morbidity: Defined by the Post Operative Morbidity Survey (POMS) before (preoperative) and after (postoperative days 3 and 7) surgery. The POMS is an 18-item survey which examines nine domains (pulmonary, infection, renal, gastrointestinal, cardiovascular, neurological, haematological, wound, pain) of postoperative morbidity.[2] The POMS is a reliable and valid measure of short-term postoperative morbidity following major surgery.²⁰ The hospital electronic patient management system will be used to prospectively record POMS on postoperative days 0 (preoperative), 3 and 7. Clavien-Dindo grades for complications during hospital stay will also be reported.

Opiate use: Opiate consumption [expressed as morphine equivalents] before and for three days after surgery.

Explanatory measures

Autonomic function, as assessed by time and frequency domain measures of heart rate variability 10 minutes before and 10 minutes after each stimulation session, before and after surgery.[3]

Sample size and randomisation

Sample size calculation

Consensus perioperative guidelines recommend that the Visual Analogue Score should be used to assess pain intensity.[4] 72 patients are required to have a 90% chance of detecting, significant at the 1% level, a decrease in mean VAS (the primary outcome measure) from 34mm in the control group to 23mm in the experimental group after surgery (standard deviation of outcome 12mm). Allowing for 10% dropout per group, a final sample size of 86 participants is required, analysed by intention to treat.

Randomisation procedure

Randomisation will occur after the participant has provided informed consent before the surgical procedure is due to start. Participants are randomly assigned (1:1) by block randomisation to receive stimulation or sham stimulation to ensure a balance in sample size across groups over time (Power

Analysis & Sample Size (PASS) 2021, Utah, USA). Investigators will log on to a secure web-based randomisation file to obtain a unique patient identification number and allocation to a treatment group.

Analysis methods

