The effect of stimulation/sham on time and frequency domain measures of heart rate variability 10 minutes before and 10 minutes after each stimulation session, before and after surgery.[3] . Repeat-

measures ANOVA will be used (group: stimulation/sham X experimental timepoint X before/after surgery), with post hoc Tukey-Kramer testing.

Exploratory analyses

Exploratory analyses will be repeated to examine the relationship between autonomic parameters and achieving MCID, independent of group allocation to stimulation/sham.

Sensitivity analysis

The amount of missing primary outcome data is anticipated to be minimal but will be accounted for in a sensitivity analysis if missing data is greater than 5%.

Other analyses, data summaries and graphs

Clinical management

Clinical management for sham/stimulation groups will be summarised but not subjected to statistical testing. Numbers (%) and means (SD) or medians (IQR) will be provided separately for each group. The sham/stimulation groups will be compared for the following clinical management characteristics:

- Anaesthetic technique
- level of care on the first night after surgery

Process measures

Summary measures will be presented separately for each treatment group. All patients with recorded data will be included in the summary. Formal statistical analysis will not be performed. Duration of hospital stay after surgery (days) will be summarised using median (IQR).

Safety analyses

Adverse events and serious adverse events will be presented as a number (%) by treatment group. All patients with a recorded outcome will be included in the summary. In addition to this, 'other' adverse events will be reported separately if prevalence is more than 5% across all participants in the trial.

- Arrhythmia
- Headache
- Pain
- Skin irritation at the stimulation site
- Dizziness
- Other
- None

Protocol deviations

Numbers and percentages of protocol deviations will be reported. Protocol deviations will be reported as participants who stopped therapy either during the stimulation period, before and/or after surgery. Stimulation current, as applicable, will be reported to demonstrate variation in protocol parameters.

Complications within 30 days after surgery

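### The only planned analysis linking heart rate variability to pain uses a yes/no 10 mm cut, although VAS change in mm exists for the same sessions; a mm-scale model would be a cheap gain in power of uncertain size.

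*SAP*

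**What the plan says.** The SAP, under Exploratory analyses, plans one link between autonomic function and pain: "Exploratory analyses will be repeated to examine the relationship between autonomic parameters and achieving MCID". The sentence adds that this is to be done independently of the allocated arm. The SAP names no test or model for this and gives no expected strength of association.

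MCID is defined under Secondary outcome measures, and again under Analysis of secondary outcomes, as a responder outcome: "The proportion of participants who achieve a minimally clinical relevant reduction >10mm using the 100 mm pain Visual Analogue Score". The same two sections also plan to use the change in mm, for the outcome that groups patients by how severe their pain is. There the SAP says: "Absolute changes in pain score before and after sham/stimulation will be compared before and after the period of stimulation in each group".

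HRV is recorded around the same sessions. Explanatory measures describes it as "heart rate variability 10 minutes before and 10 minutes after each stimulation session, before and after surgery". The repeated-measures ANOVA planned there has group, timepoint and before/after surgery as its factors. It contains no pain variable.

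**The concern.** HRV is the trial's named explanatory variable, and the exploratory analysis is the only one that can show whether a change in autonomic function goes with a change in pain. With the pain side reduced to yes/no at 10 mm, a fall of 0 mm counts the same as a fall of 10 mm, and a fall of 11 mm the same as one of 50 mm.

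The 10 mm threshold is cited as a clinically important difference. That is a good reason to report a responder proportion. It gives no reason to measure an association with HRV through the cut when the mm values are available for the same patients and sessions. At stake is the chance of detecting a moderate association with about 72 evaluable patients.

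**Working it through.** **Inputs from the SAP.** Sample size calculation: "72 patients are required to have a 90% chance of detecting, significant at the 1% level, a decrease in mean VAS", "from 34mm in the control group to 23mm in the experimental group after surgery", with "standard deviation of outcome 12mm". Allocation is 1:1. General analysis principles sets 5% for all analyses. Two-sided p-values are stated there for the primary, secondary and process measures, and I assume the same here.

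**The plan's own figure.** n per arm = 2(z₀.₉₉₅ + z₀.₉₀)² × SD²/Δ² = 2 × (2.576 + 1.282)² × 144/121 = 35.4, so 36 per arm and 72 in all. The stated 72 reproduces. It was derived for the primary outcome; no power is stated for the exploratory analysis.

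**Inputs the SAP does not give (assumed).**
- Within-arm correlation r between HRV change and VAS change: 0.1 to 0.4.
- SD of VAS change: 12 × √(2(1 − ρ)) for a before/after correlation ρ. This is 12 mm at ρ = 0.5 and 7.6 mm at ρ = 0.8. It borrows the SD of the primary outcome.
- Mean fall on sham: 0 to 10 mm.
- Extra mean fall on stimulation: 0 to 11 mm.
- One session per patient, one HRV measure, normal data.

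**Step 1: closed form, ignoring arm.** Power for a correlation is about Φ(atanh(r) × √(N − 3) − 1.96). Cutting the outcome at responder rate p multiplies r by φ(z_p)/√(p(1 − p)). For N = 72, √69 = 8.307, and r = 0.3:

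| Pain variable | Multiplier | Effective r | Power | Loss (points) |
|---|---|---|---|---|
| Change in mm | 1 | 0.300 | Φ(2.571 − 1.96) = 73% | – |
| Yes/no, p = 50% | 0.798 | 0.239 | Φ(2.03 − 1.96) = 53% | 20 |
| Yes/no, p = 20% | 0.700 | 0.210 | Φ(1.77 − 1.96) = 42% | 30 |
| Yes/no, p = 10% | 0.585 | 0.175 | Φ(1.47 − 1.96) = 31% | 42 |

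(Losses are taken before rounding.) The squared multiplier is the relative efficiency: 0.64, 0.49 and 0.34. So 72 patients cut at these rates carry the information of about 46, 35 and 25 patients analysed in mm.

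**Step 2: what responder rates are plausible.** P(fall > 10) = Φ((mean fall − 10)/SD). With no fall and SD 7.6 this is Φ(−1.32) = 9%. With a mean fall of 10 mm it is 50%. With a mean fall of 11 mm and SD 12 it is Φ(0.08) = 53%. The assumed sham fall therefore matters: at zero it makes sham responders rare and the split lopsided, which raises the loss.

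**Step 3: simulation with arm in both models.** 36 per arm, HRV change z ~ N(0,1), VAS fall = sham fall + extra fall × arm + SD × (r z + √(1 − r²) e). The mm analysis tests z in fall ~ arm + z. The cut analysis tests MCID in z ~ arm + MCID. Ranges run over the assumed SDs, sham falls and extra falls:

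| r | Power in mm | Loss from the cut (points) |
|---|---|---|
| 0.1 | about 13% | 2 to 6 |
| 0.2 | about 39% | 12 to 22 |
| 0.3 | about 73% | 19 to 42 |
| 0.4 | about 94% | 15 to 45 |

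At r = 0.3 the loss is about 25 to 42 points with no sham fall and 19 to 32 with a sham fall of 5 to 10 mm. Simulation error leaves the ends of these ranges uncertain by a point or two. Steps 1 and 3 agree closely, so the loss does not hinge on whether the SAP's phrase about independence from allocation means adjusting for arm or ignoring it.

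**The case against.** The strongest reply is that the SAP asks a legitimate question. Whether autonomic measures differ between patients who do and do not get clinically relevant relief is not the same question as a slope per mm. MCID is a prespecified secondary outcome with a cited threshold, and this analysis is labelled exploratory and supports no confirmatory claim. That stands. It is why the responder comparison should be kept, and why the point is minor.

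It is also fair that the size of the loss is not a property of the plan. A reader might infer a flat loss of some 20 to 45 points. The SAP does not support that: at r = 0.2 the loss is about half as large, at r = 0.1 it is 2 to 6 points, and the upper end depends on assuming little or no fall on sham. At r = 0.2 or below the mm analysis itself has at most about 40% power, so changing scale would not rescue the question.

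A reader might also infer a floor problem, because patients who start at 10 mm or less cannot achieve MCID. The SAP gives no pre-session VAS distribution; the 34 and 23 mm are planned outcome means after surgery. Such a patient cannot fall by more than 10 mm on the mm scale either, so the floor does not separate the two analyses.

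Nor does the SAP say that a null result would be read as showing no autonomic link.

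Two limits of the working remain. It models one session and one HRV measure, and it leaves out the pre-session VAS covariate recommended below. Treating both sessions as independent (N = 144, ignoring arm) would give a loss of about 13 to 40 points at r = 0.3. Appendix 1 describes MCID on a 0 to 100 mm scale, which sits awkwardly with a responder outcome, but achieving it is plainly yes/no.

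**Conclusion.** The point holds as a conditional one. The SAP's only HRV–pain analysis uses a dichotomised pain outcome while the change in mm is available for the same sessions, and every scenario tried showed some loss of power. Under the assumptions listed, the loss is substantial for a moderate association (r of 0.3 to 0.4), moderate at r = 0.2 and negligible at r = 0.1. The SAP gives no correlation, responder rate or sham fall with which to narrow this. It is an inexpensive improvement to an unpowered exploratory analysis. It is not an error, and it does not touch the primary or secondary results.

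**What to change.** Under Exploratory analyses, make the lead analysis a linear model of VAS change in mm over a session on HRV change over the same session, with pre-session VAS and arm as covariates. If the sessions before and after surgery are pooled, allow for repeated sessions within a patient, for example with a patient random effect. Keep HRV by MCID achieved or not achieved as a supporting display.

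The cost is a sentence or two of SAP text and one extra regression per HRV measure, on data already collected. The small downside is that the lead association is expressed per mm rather than by responder status; the retained display covers that.

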General analysis principles

Analyses will follow the intention-to-treat principle: all randomised patients with a recorded outcome will be included in the analysis and analysed according to the treatment to which they were randomised [5, 6]. Patients will be included in the analysis, regardless of whether the treatment they received was compliant with the protocol. Definitions of what constitutes a recorded outcome for each outcome can be found in Appendix 1. Patients with missing outcome data will be excluded from the analysis. Missing data for baseline covariates to be included in the analysis model will be accounted for using mean imputation for continuous variables and the missing indicator approach will be used for missing data for categorical variables [7, 8].

For the analysis of the primary outcome, each secondary outcome, and all process measures, we will present the following information:

The number of patients included in each analysis, by treatment group

A summary statistic of the outcome (e.g. mean (SD), number (%)), by treatment group

The estimated treatment effect

A 95% confidence interval for the estimated treatment effect

A two-sided p-value

For all analyses, a significance level of 5% will be used.

Representativeness of patients

A log of eligible patients not recruited to the trial will be kept. Reasons for non-participation will be categorised and summarised. Participation in the trial, treatment allocation and completeness of follow-up will be illustrated by a CONSORT flow diagram [9].

Baseline characteristics

Baseline characteristics will be summarised for each treatment group by the mean and standard deviation or median and interquartile range for continuous variables, and the number and percent for categorical variables. The following baseline characteristics will be summarised by treatment group:

- Demographic: age (years), gender (male/female)
- Co-morbid disease: Hypertension; Ischaemic heart disease; Cardiac failure; Cardiac valvular disease
- Stroke/TIA; Peripheral vascular disease; Diabetes mellitus, type I; Diabetes mellitus, type II ; COPD; Asthma
Smoker; Interstitial or other respiratory disease; Liver cirrhosis; GI pathology-other; Osteoarthritis;
Rheumatoid arthritis; Inflammatory disease; Active cancer; Previous cancer
- ASA grade

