- Medications: Statin; Anticoagulant; Antiplatelet; Beta-blocker; Calcium channel antagonist; Heart rate limiting calcium channel antagonist; Doxazosin; Diuretic; Nitrate; Angiotensin converting enzyme inhibitors; Angiotensin II Receptor Blockers; Other hypertensives; Other heart failure Rx; Digoxin/anti-arrhythmic; Other Rx Asthma Rx; Opioids-oral; Opioids- parental; NSAIDs; Paracetamol' Steroids; Metformin; Insulin; Any other diabetic medication
- Pre-operative blood test results (within 1 week before surgery or most recent): Haemoglobin; Serum Albumin; Creatinine; white cell count; Neutrophil count; Lymphocyte count; CRP
- Anxiety: GAD-7 and Amsterdam preoperative anxiety score.

Analysis software

All analyses will be conducted in NCSS 2021 (NCSS 2021 Statistical Software (2021). NCSS, LLC. Kaysville, Utah, USA, ncss.com/software/ncss).

Analysis of primary outcome

Primary analysis

Difference in absolute pain score 24h after surgery, assessed by 100mm visual analogue score (VAS), under the ITT principle [10]. Repeat-measures ANOVA will be used to compare VAS before versus after stimulation/sham, with post hoc Tukey-Kramer testing.

Analysis of secondary outcomes

Minimally clinical relevant reduction before and 24h after surgery: The proportion of participants who achieve a minimally clinical relevant reduction >10mm using the 100 mm pain Visual Analogue Score will be compared before and after the period of stimulation in each group, before and after surgery.[1] Paired t-test will compare between sham and stimulation groups.

VAS stratified by pain intensity: Absolute changes in pain score before and after sham/stimulation will be compared before and after the period of stimulation in each group before and after surgery, stratifying for mild, moderate, and severe pain intensity before the intervention. Repeat-measures ANOVA will be used to compare VAS before versus after stimulation/sham, with post hoc Tukey-Kramer testing.

Postoperative morbidity: Absence of POMS will be compared between groups serially [time to become free of morbidity after surgery]. Individual POMS will be reported in a separate table but not tested formally.

Opiate use: Opiate consumption [expressed as morphine equivalents] will be presented before and for three days after surgery, between stimulation/sham, but not tested formally.

Explanatory measures

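### The exploratory analysis of heart rate variability against MCID most naturally reads as pooling the arms; treatment arm should be named as a covariate

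*SAP*

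**What the plan says.** The SAP gives this analysis one sentence, under Exploratory analyses: the "relationship between autonomic parameters and achieving MCID, independent of group allocation to stimulation/sham". It names no model, arm term, within-arm estimate, HRV index or timepoint.

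Four other places bear on it:

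- The SAP's study objectives list "heart rate variability [explanatory variable" among the secondary objectives.
- The Explanatory measures paragraph of the analysis section sets the recording times: "heart rate variability 10 minutes before and 10 minutes after each stimulation session, before and after surgery". It plans a repeated-measures ANOVA with factors "group: stimulation/sham X experimental timepoint X before/after surgery". That model contains arm, but it tests the effect of arm on HRV and does not address the link between HRV and MCID.
- Analysis of secondary outcomes defines MCID by the proportion who "achieve a minimally clinical relevant reduction >10mm using the 100 mm pain Visual Analogue Score", before and after the stimulation period.
- General analysis principles states: "For all analyses, a significance level of 5% will be used".

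**The concern.** The exploratory sentence comes directly after an ANOVA that has arm as a factor. It says that analyses will be repeated and sets group allocation aside. An analyst would most naturally put both arms together and relate HRV to MCID status.

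Arm is then a possible common cause. The trial is designed to detect an effect of stimulation on pain, and it also tests for an effect on HRV. If both effects exist, stimulated patients will tend to have shifted HRV and will also include more MCID responders. The pooled data then show HRV and MCID moving together even if, among patients with the same allocation, HRV says nothing about who gets relief. The artefact is therefore most likely when the treatment works.

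What is at stake is how one exploratory result is read. Because HRV is labelled explanatory, a reader could take a pooled association as a sign of how stimulation relieves pain, when it may only restate that stimulation does two things.

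**Working it through.** **The plan's own figure.** The SAP states no figure for this analysis. The nearest is the sample size: "72 patients are required to have a 90% chance of detecting, significant at the 1% level", for a fall in mean VAS "from 34mm in the control group to 23mm in the experimental group after surgery", SD 12 mm. With a two-sided 1% level, n per arm = 2 × (2.576 + 1.282)² × 12² / 11² = 35.4, so 36 per arm and 72 in total. This reproduces.

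**Inputs for the check**

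- From the SAP: between-arm difference 34 − 23 = 11 mm; SD of the outcome 12 mm; MCID threshold above 10 mm; 1:1 allocation; 86 randomised with 10% dropout, so 43 × 0.9 = 38.7, taken as 39 per arm; 5% significance level.
- Assumed: mean reduction across the session of 11 mm on stimulation and 0 mm on sham; SD of that reduction 12 mm, or alternatively 17 mm (pre and post scores each with SD 12 mm and uncorrelated, √(2 × 12²) = 17.0); stimulation shifts HRV by d = 0.3, 0.5, 0.8 or 1.0 SD; no link between HRV and MCID within either arm.

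**Step 1: MCID rates under these assumptions**

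- SD 12 mm: stimulation P(Z > (10 − 11)/12) = P(Z > −0.083) = 0.533; sham P(Z > 10/12) = P(Z > 0.833) = 0.202.
- SD 17 mm: stimulation P(Z > −0.059) = 0.523; sham P(Z > 0.589) = 0.278.

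**Step 2: correlation created by pooling.** With equal arms, and p̄ the mean of the two MCID rates,

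r = [d (p₁ − p₀)/4] / √[(1 + d²/4) p̄(1 − p̄)].

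For d = 0.8 and SD 12 mm: p₁ − p₀ = 0.331 and p̄ = 0.368. The numerator is 0.8 × 0.331/4 = 0.0662. The denominator is √(1.16 × 0.2325) = 0.519. So r = 0.127, although the within-arm correlation is zero.

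**Step 3: chance that the pooled test is significant.** With N = 78, the Fisher z statistic has mean atanh(0.127) × √75 = 1.11. The two-sided rejection probability is P(Z > 1.96 − 1.11) + P(Z < −1.96 − 1.11) = 0.198 + 0.001, or about 20%.

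**Step 4: all shifts.** Simulation at 39 per arm, no within-arm link, nominal 5%:

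| HRV shift (SD) | Pooled, SD of change 12 mm | Pooled, SD of change 17 mm | Arm in the model |
|---|---|---|---|
| 0.3 | about 7% | about 6% | about 5% |
| 0.5 | about 11% | about 8% | about 5% |
| 0.8 | about 20% | about 13% | about 5% |
| 1.0 | about 28% | about 16% | about 5% |

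The approximation in steps 2 and 3 agrees with the simulation to within about one percentage point in every pooled cell.

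**Step 5: other assumed MCID rates, 43 per arm.** With 30% v 50% and a 0.3 SD shift, pooled rejection is 5.8%. With 30% v 60% and 0.5 SD it is 10.2%. With 20% v 70% and 1.0 SD it is 56.3%. Arm-adjusted rates in these cases are 4.8% to 5.6%. If stimulation affects only HRV (30% v 30%, 0.5 SD) or only MCID (30% v 60%, no shift), the pooled rate is 4.5% or 5.3%, so both effects are needed.

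**The case against.** Five points can fairly be made in the plan's defence.

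- **The wording does not fix pooling.** Statisticians also write that an association is independent of a factor when they mean adjusted for it, and on that reading the plan already intends the right model. This stands as a limit on the claim: a reader might infer that the SAP commits to an unadjusted analysis, and it does not say so. It does not remove the need for a change, because two analysts could comply with the sentence, one with an arm term and one without.
- **The MCID rates are not the plan's.** A reader might infer that 53% v 20% follows from the sample size paragraph. It does not. That paragraph gives absolute postoperative scores by arm and the SD of those scores, whereas MCID is a within-patient reduction across a session. The 0 mm sham reduction and the SD of change are assumptions. This stands, and it is why the result is shown as a range.
- **The HRV timepoint is open.** HRV recorded before the first session cannot have been altered by stimulation, so relating it to MCID carries no such bias, pooled or not. This stands; the concern is confined to HRV that stimulation could have shifted.
- **No mechanism is claimed.** A reader might infer from the explanatory label that the trial will present HRV as the route to pain relief. The SAP mentions neither mediation nor mechanism and calls this analysis exploratory. A pooled association would also be real as a description of the whole sample; it would mislead only if taken to hold within arms.
- **The effects by arm will be visible elsewhere.** The HRV ANOVA includes group and MCID is reported by arm, so a careful reader could see whether stimulation moved both. That helps interpretation but does not supply the adjusted estimate.

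**Conclusion.** The point holds as a small, free improvement to one exploratory analysis. The sentence leaves the model open and most naturally points to pooling. If stimulation alters both post-session HRV and pain, the pooled test finds an HRV-MCID association too often for anyone who reads it as a within-arm link.

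Under the assumed rates of 53% v 20%, the excess over 5% is slight for a 0.3 SD shift (about 7%) and material at 0.8 to 1.0 SD (about 20% to 28%). A larger SD of change reduces it to about 13% to 16% for those same two shifts. These figures depend on HRV and MCID effects that the SAP does not give. The direction of the problem, and its removal by an arm term, do not depend on the particular values.

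The documents do not support the stronger conclusion that the plan has chosen a confounded analysis in order to claim a mechanism. No primary or secondary result is affected.

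**What to change.** In Exploratory analyses, replace the closing words on group allocation with: estimated with treatment arm included as a covariate, with within-arm estimates also shown. Add that the result will be reported as an exploratory association and not as evidence of mechanism; an arm term removes confounding by allocation, but HRV and pain may share other causes. It would help to name in the same sentence the HRV measure and recording time to be used, since the concern does not apply to HRV recorded before the first session.

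The cost is one sentence and one model term. No new data are needed and no other analysis changes.

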≥1 treatment deviation		
Current before		
Current after		
Other deviation		

Table 4: Primary and secondary outcomes.

Outcomes	Number of patients with available data and included in analysis - no. (%)		Summary measure		Treatment effect (95% CI)	P-value
	Sham (n=XX)	Stimulation (n=XX)	Sham	Stimulation		
Primary outcome						
VAS 24h after surgery						
Secondary outcomes						
MCID						
VAS before surgery						
VAS [pain intensity]						
Opiate use						

Table 5: PostOperative Morbidity survey: reported before surgery, 3 and 7 days after surgery.

Complication	Number of patients with available data - no. (%)		Summary measure	
	Sham (n=XX)	Stimulation (n=XX)	Sham	Stimulation
De novo requirement for supplemental oxygen.				
Respiratory support.				
Currently on antibiotics.				
Temperature >38°C/ blood cultures in last 24h.				
Oliguria (< 500 mL/day),				
Serum creatinine (>30% from baseline value)				
Unable to tolerate normal enteral diet				
Nausea/vomiting.				
Myocardial infarction or ischemia				
Hypotension (drug therapy/fluid >200 mL/h)				
Atrial or ventricular arrhythmia				
Pulmonary edema				

De novo focal neurological deficit				
Coma.				
Confusion/delirium.				
Wound dehiscence requiring surgical exploration				
Wound drainage/pus.				
Blood, platelets, fresh frozen plasma or cryoprecipitate.				
Surgical wound pain-parenteral opiates				
Regional anesthesia.				
Not mobilising alone				
None				

Table 6: Process measures

Process measures	Number of patients with available data - no. (%)		Summary measure	
	Sham (n=XX)	Stimulation (n=XX)	Sham	Stimulation
Re-admission to hospital within 30 days of surgery – no. (%)				
Duration of hospital stay after surgery (days) - Median (IQR)				
Number of patients admitted to a critical care unit - no. (%)				

Table 7: Adverse events

Adverse Events - no. (%)	Sham (n=XX)	Stimulaton (n=XX)
Patients with ≥ 1 adverse event		
Total number of adverse events		
Type of adverse events		
Arrhythmia ^a		
Headache		
Pain ^b		
Skin irritation at the stimulation site		
Dizziness		
Other		
None		

^a Defined as clinically detected arrhythmia during or after day of intervention.

^b Defined as localised pain to auricular region

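### The 5% threshold for naming an 'other' adverse event is applied to both arms pooled, so an unanticipated event in 4/43 stimulated and 0/43 sham patients would be counted but not named (minor)

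*SAP*

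**What the plan says.** The Safety analyses paragraph of the SAP (under Other analyses, data summaries and graphs) sets a general rule: "Adverse events and serious adverse events will be presented as a number (%) by treatment group". It adds that "All patients with a recorded outcome will be included in the summary". It then states a further rule for events outside the listed types, which "will be reported separately if prevalence is more than 5% across all participants in the trial". The listed types are arrhythmia, headache, pain, skin irritation where the device is applied, and dizziness.

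Table 7 in Appendix 3 follows the same layout, with one column per arm. It has rows for patients with at least one event and for the total number of events. Under "Type of adverse events" it then has the five listed types, a single undivided 'Other' row and 'None'. It has no rows for individual 'other' terms, and the SAP plans no listing of terms that fall below the threshold.

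On size and allocation, the sample size section says "a final sample size of 86 participants is required, analysed by intention to treat", and the randomisation section says "Participants are randomly assigned (1:1) by block randomisation to receive stimulation or sham stimulation".

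**The concern.** The safety table is meant to let a reader compare the arms, but the filter that decides which unlisted events are named looks at the arms combined. With 1:1 allocation, an event confined to one arm has its prevalence halved before the 5% test. The sham delivers no current, so an unforeseen effect of the current would be expected mainly in the stimulation arm. The rule is therefore least sensitive to that pattern. An event at 6% in both arms passes the filter, whereas one at 9% in a single arm does not.

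What is at stake is whether a reader of the safety table can tell what an unanticipated one-sided event was. No efficacy estimate, test or error rate depends on it.

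**Working it through.** **Inputs from the SAP.** Threshold: more than 5%, both arms pooled. Total randomised: 86. Allocation 1:1, so 86/2 = 43 per arm.

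**Inputs that are assumptions.** True event rate on stimulation 10% (7% as a second case). True sham rate 0%, 3% or 5%. The SAP gives no expected rate for unlisted events.

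**Step 1: the plan's own numbers.** With a difference of 11 mm (34 v 23), SD 12 mm, two-sided 1% level and 90% power, the normal formula gives 36 per arm, or 72, as stated. Simple inflation gives 72/0.9 = 80, not 86. The exact t-test size is 38 per arm, and 38/0.9 = 42.2, rounded up to 43 per arm, gives 86. So 43 per arm is a consistent reading of the plan.

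**Step 2: how many patients trigger naming at 43 per arm.**

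| Patients with event, all in one arm | Rate in that arm | Pooled rate | Pooled rule | Either-arm rule |
|---|---|---|---|---|
| 2 | 2/43 = 4.65% | 2/86 = 2.33% | unnamed | unnamed |
| 3 | 3/43 = 6.98% | 3/86 = 3.49% | unnamed | named |
| 4 | 4/43 = 9.30% | 4/86 = 4.65% | unnamed | named |
| 5 | 5/43 = 11.63% | 5/86 = 5.81% | named | named |

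The pooled rule needs 5 patients in total. A rule of more than 5% in either arm needs 3 in one arm.

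**Step 3: probability that the event stays unnamed.** Let X ~ Binomial(43, p) on stimulation and Y ~ Binomial(43, q) on sham, independent.

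- Pooled rule: P(X + Y ≤ 4) = Σ P(X = x) · P(Y ≤ 4 − x), for x = 0 to 4.
- Either-arm rule: P(X ≤ 2) · P(Y ≤ 2).

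For p = 0.10, P(X = 0, 1, 2, 3, 4) = 0.0108, 0.0515, 0.1201, 0.1824, 0.2027. These sum to P(X ≤ 4) = 0.5675, and the first three sum to P(X ≤ 2) = 0.1824 (equal to P(X = 3) by chance).

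- q = 0: pooled 0.5675; either-arm 0.1824 × 1 = 0.1824.
- q = 0.03: pooled 0.0108 × 0.9909 + 0.0515 × 0.9605 + 0.1201 × 0.8619 + 0.1824 × 0.6288 + 0.2027 × 0.2699 = 0.333; either-arm 0.1824 × 0.8619 = 0.157.
- q = 0.05: pooled 0.0108 × 0.9377 + 0.0515 × 0.8334 + 0.1201 × 0.6352 + 0.1824 × 0.3595 + 0.2027 × 0.1102 = 0.217; either-arm 0.1824 × 0.6352 = 0.116.

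| Sham rate (assumed) | Pooled rule | Either-arm rule | Gap |
|---|---|---|---|
| 0% | 57% | 18% | 39 points |
| 3% | 33% | 16% | about 18 points |
| 5% | 22% | 12% | about 10 points |

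At a true 7% on stimulation and 0% on sham, the probabilities are 82% and 41%.

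**Step 4: does it depend on 43 per arm?** With 36 per arm, 3/36 (8.3%) v 0/36 is 3/72 = 4.17% and unnamed, and 4/72 = 5.56% is named. At 10% v 0%, the probabilities of staying unnamed are 51% and 11%. The exact counts shift but the pattern does not.

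**The case against.** The strongest reply is that little is lost. The 5% sentence adds to an unconditional presentation of adverse and serious adverse events by arm. A 4 v 0 excess still enters three by-arm rows of Table 7: patients with any event, total events and 'Other'. The five foreseeable types have their own rows at any frequency. All of this stands. A reader might infer that the rule hides a one-sided event altogether, or that it affects device-related events in general. The SAP supports neither: the count remains by arm, only the name is lost, and only unlisted events are affected.

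A reader might also suppose that 'Other' is swollen by routine postoperative events, so that an excess would be drowned. The SAP does not say so. Postoperative Morbidity Survey items are tabulated by arm in Table 5, and 30-day Clavien-Dindo complications are summarised by allocation. Nothing says these are counted again under 'Other', so the point must stand without that dilution, and it does.

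The 0% sham rate is the most favourable case for the concern. With background events in sham the gap shrinks, as the table of sham rates shows.

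The sentence could also be read as applying 5% to the 'Other' category as a whole. The denominator would still be pooled, but the category could reach 5 patients through several different events and then be broken down. That ambiguity is real, and clearer wording would remove it.

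Finally, any cut-off leaves some events unnamed: the alternative still leaves 2/43 v 0/43. And 4/43 v 0/43 has a two-sided Fisher p of 0.12, so this is not a missed significant result. Both statements are correct. The issue is visibility in a table that the SAP plans as descriptive.

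**Conclusion.** The point holds as a minor one. As written, the rule can leave an unanticipated event unnamed when it occurs in up to 4/43 (9.3%) of stimulated and no sham patients. At a true 10% on stimulation, moving from the pooled to an either-arm threshold lowers the chance of that by about 10 to 39 percentage points for sham rates between 5% and 0%.

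This rests on 43 per arm with recorded safety data, on independent binomial counts, on the assumed event rates, and on reading the 5% as applying to each event rather than to the whole category.

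It does not extend to serious adverse events. A reader might infer from the missing serious-event row in Table 7 that the threshold affects them too, but the SAP presents them by arm without any threshold. It also has no bearing on the primary or secondary analyses.

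**What to change.** In Safety analyses, replace the threshold sentence with: *Any other adverse event will be reported separately, by arm, if it occurs in more than 5% of participants in either treatment group.* Add matching rows beneath 'Other' in Table 7. Starting the sentence with 'any' also settles that the threshold applies to each event and not to the category as a whole.

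The cost is one sentence and a few table rows, with no new data. The downside is that some rows will rest on as few as 3 patients at 43 per arm, or 2 if an arm has 39 or fewer with data (2/39 = 5.1%), so they should be read as description only.
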